5.1	Eligibility Criteria	18
5.1.1	Inclusion Criteria	18
5.1.2	Exclusion Criteria	19
5.2	Study Setting and Sample Identification	19
5.3	Sampling	20
5.4	Recruitment	20
5.5	Consent	21
5.6	Participant Compensation	21
6.	Statistics and Analysis	21
6.1	Data Analysis	22
7.	Ethical and Regulatory Compliance	23
7.1	Risks and Burdens to Participants and Researchers	23
7.2	Research Ethics Committee (REC) and Other Regulatory Reviews &	23
	Reports	
7.2.1	NHS REC Reviewed Research	23
7.3	Amendments	24
7.4	Peer Review	24
7.5	Patient and Public Involvement	24
7.6	Protocol Compliance	25
7.7	Data Protection and Participant Confidentiality	25
7.7.1	Data Management	26

Protocol FINAL v. 1.0

Date: 02/Oct/2024

IRAS ID: 322953

7.7.2	Redcap	27
7.8	Indemnity	27
7.9	Monitoring	27
7.10	Access to the Final Study Dataset	28
8.	Safety Reporting	28
9.	Dissemination	29
9.1	Dissemination Policy	29
9.1.1	Publication and Dissemination (REDCap)	30
9.2	Authorship Eligibility Guidelines and Any Intended Use of Professional Writers	30
10.	Archiving	30
11.	References	31
Appendix 1	Interview guide	33
Appendix 2	KOOS-PF and VAS _{NA} questions	34

Date: 02/Oct/2024 IRAS ID: 322953 Protocol FINAL v. 1.0

Key Study Contacts

Chief Investigator	[name] Professor of Clinical Physiotherapy [name] Email: [contact]
Study Contact for Enquiries	[name], Project Manager, University of Manchester, Email: [contact]
Sponsor	[name], Manchester University NHS Foundation Trust, [name] Email: [contact] [contact]
Funder(s)	National Institute for Health Research (NIHR) [name] Email: [contact]
Statistician	[name] – Manchester University NHS Foundation Trust. Email: [contact]
Key Protocol Contributors	[name]: [contact] [name] [name]: [contact] [name]: [contact] [name]: [contact]
Committees	Trial Management Group: [name] Email: [contact]

Study Summary

Study Design	Feasibility study and qualitative assessment of an intervention			
Study Participants	Adults aged ≥ 40 years with patellofemoral knee osteoarthritis			
Planned Size of Sample	WP2: N=30 WP3: N≈15			
Recruitment Period	6 months			
Follow Up Period	3 months			
Overall Study Duration	16 months			
Research Question/Aim(s)	To determine whether patellar taping is feasible and acceptable as part of a treatment package for painful patellofemoral joint osteoarthritis (PFJOA) If feasible and acceptable, to plan a full, definitive randomised controlled trial (RCT) to determine long-term clinical effectiveness.			
i) To pa		To assess recruitment to the study and participant retention To determine whether the tape can be applied by participants correctly at home. To determine adherence to the taping intervention. To assess how to optimise adherence to taping over an extended period. To determine participants views about the acceptability of taping. To determine whether participants experience a reduction in pain in response to tape. To determine a primary outcome for a large scale RCT and to inform the sample size calculation.		
Primary Outcome Measures		Primary Endpoints		
(i) WP2: To assess recruitment to the study and participant retention: Uptake - number recruited and % drop out rate.		WP2: Participant uptake - number recruited per month and % drop out rate.		
WP3: Report on participant experie taping and the trial process.	ences of	WP3: Qualitative Report.		

Explore facilitators and barriers to adherence. Evaluate the performance of the participant treatment package.	
Secondary Outcome Measure(s)	Secondary Endpoint(s)
(ii) To determine whether the tape can be applied by participants correctly at home - Clinical checks at 2 weeks recorded on the Clinical Report Form.	
iii) Adherence to wearing the tape: Number of returned/counted tapes, number of days per week worn and the average hourly use.	 Intervention adherence – number of tapes returned or counted at week 2, 6 and 12. Number of days that participant reports wearing the tape at weeks 2, 6 and 12. Number of hours the participant reports wearing the tape daily at weeks 2, 6 and 12.
(iv & v) To assess how to optimise adherence top taping over an extended period and to determine participant views about the acceptability of prolonged taping: Participant interviews in WP3	Qualitative analysis of interviews.
(vi) Effect of intervention, reduction in pain	 Pain relief during nominated activity (VAS_{NA}) – the difference between
 (a) Knee pain measured by VAS_{NA} at baseline, 2, 6 & 12 weeks (b) Knee pain and knee function measured by KOOS-PF at baseline, 2, 6 & 12 weeks. 	baseline and 12 week measures. 2. KOOS-PF – the difference between baseline and 12 week measures.
(vii) To determine a primary outcome for a large scale RCT and to inform sample size: Analyses of quantitative data in (vi. a & b)	

Funding and Support in Kind

Funder(s)	Financial And Non-Financial Support Given Detail financial and non-financial support given by each organisation listed
National Institute for Health	The total amount awarded under this Project to all the
Research (NIHR)	Parties from the Funder shall be £249,419.00

Role of Study Sponsor and Funder

Manchester University NHS Foundation Trust (MFT) is acting as sponsor for this study and is assuming overall responsibility for the initiation and management of the study. The Trust will provide permission to conduct the research and monitor the progress of that research. The research team all hold substantive or honorary contracts with the Trust and therefore the sponsor has influence over all aspects of the study design, conduct, data analysis and interpretation, manuscript writing, and dissemination of results which are the responsibility of the research team.

Roles and Responsibilities of Study Management Committees/Groups & Individuals

- Trial Management Group (TMG): Monthly team meetings held online or in person. These
 meetings are to update the study team, highlight any risks or issues and include mitigation
 plans, raise any amendments to the study and ensure timelines and task deadlines are
 met
- 2. PPIE [name] is our PPIE Co-Applicant. She attends the TMG meetings and provides feedback on all aspects of the project.

Key Words: Patellofemoral Joint Osteoarthritis (PFJOA)

Feasibility and acceptability

Taping

Intervention

AbbreviationsAbbreviation	Definition		
MFT	Manchester University NHS Foundation Trust		
REC	Research Ethics Committee		
TMF	Trial Master File		
PPIE	Patient and Public Involvement and Engagement		
CI	Chief Investigator		
PFJOA	PatelloFemoral Joint OsteoArthritis		
OA	Osteoarthritis		
RCT	Randomised Controlled Trail		
FDA	Food and Drug Administration		
NSAIDS	Non-Steroidal Anti-Inflammatory Drugs		
HTA	Health Technology Assessment		
WP	Work Packages		
VAS	Visual Analogue Scale		
KOOS-PF	Knee Injury and Osteoarthritis Outcome Score - PatelloFemoral		

Study Flow Chart

TAPE-it WP2 Clinical Trial & WP3 Acceptability Patient Flow

TIMELINE (WEEKS)

First Recruitment Approach

MLCO Clinicians refer potentially eligible patients with PFJOA to study team via online Trust system

Patients given Patient Information Sheet (PIS)

Osteoarthritis (OA) is a leading cause of knee pain and disability affecting one in eight men and women aged over 50 years (1) and is associated with large healthcare and personal costs (2). There is no cure, little effective treatment and none proven that delays the disease progressing. Patellofemoral joint osteoarthritis (PFJOA) is a significant source of knee pain, yet it receives relatively little attention (3), despite being associated with high levels of pain, stiffness and functional limitation (4, 5). PFJOA has only recently been recognised as a distinct subgroup of knee OA. The prevalence for PFJOA is about 25% (95% CI: 15–37%) in population-based cohorts and 39% (95% CI: 25–54%) in symptom-based cohorts. Approximately half those with radiographic knee OA have some degree of PFJOA. In particular, females aged ≥50 years appear to have a higher prevalence of PFJOA (41%) than their male counterparts (23%) (6). Also, PFJOA tends to affect younger adults more than generalised knee OA so it is plausible that burden of disease measures, such as years lived with disability, would be higher in PFJOA than generalised knee OA (6).

Targeted interventions for PFJOA are required because it differs from tibiofemoral OA (3). Our previous work on PFJOA (7) showed significant benefits of a knee brace for this condition. However, two thirds of patients had difficulty wearing the brace, in part due to fitting issues causing discomfort and due to its appearance, both of which affected treatment adherence and treatment efficacy. Patellar taping is a low-cost treatment commonly used by physiotherapists and other clinicians in the short-term to ease joint pain. We want to test the feasibility of a taping intervention as part of a long-term treatment package for PFJOA which acts similarly to a brace but addresses the fitting and appearance problems posed by brace therapy and can be individualised to address patients' specific symptoms, unlike knee braces. The medical tape used is widely used in UK clinical practice and is FDA approved and CE-marked. Dependent upon the results, this feasibility study will inform the development of a Health Technology Assessment (HTA) application for a large randomised controlled trial looking at the cost effectiveness of a taping intervention in PFJOA.

Non-pharmacological, self-managed treatments (e.g. weight control and structured exercise) are important and valued by patients (8). Current management of knee OA focuses on reducing pain. However, patients are often reluctant to take analgesia or NSAIDs (9) due to lack of efficacy or significant toxicities. Our taping intervention could provide a safe, effective, and low-cost non-pharmacologic treatment in primary care to ameliorate clinical symptoms of pain and dysfunction. Five patients in a group convened for this application told us that a study on taping would be important for those with painful PFJOA and agreed with the benefits listed above.

Patellar taping is a well-established and successful intervention in physiotherapy practice for non-arthritic patellofemoral pain (10) or anterior knee pain (11-14), a condition affecting mostly young women. Data from our recent systematic review suggest that patellar taping may also be beneficial for older people with symptomatic PFJOA (15). The two trials to date (16, 17) on taping efficacy, however, have been short term (only up to 3 months) whilst this is a chronic condition. Additionally, these previous trials required physiotherapists applying taping treatment to patients

in a formal clinic setting and did not test the feasibility of having the patient administer the tape themselves in their own home settings.

Our study will be novel in terms of the condition treated and the method of participant self-application. The effectiveness of tape as part of a treatment package for PFJOA remains uncertain and a definitive randomised controlled trial is needed. Such a trial needs to be informed by evidence that patients with PFJOA can apply the tape, and that they will wear it over an extended period. We also need to know how symptoms, including pain, change in participants who use the tape. Such data are lacking for which further research is required.

2. Rationale

Patellofemoral joint osteoarthritis (PFJOA) has only recently been recognised as a distinct subgroup of knee OA. It is a significant source of knee pain, yet it is often overlooked despite being associated with high levels of pain, stiffness and functional limitation. In our previous trial on PFJOA using sleeve knee braces the majority of patients found adherence difficult due to the braces being uncomfortable, bulky and awkward to wear. A different device, sports tape, may have several advantages over knee braces such as being individualised to each person's knee shape, slim to wear under tight clothing and comfortable for long-term use.

Patellar taping is commonly used by physiotherapists and others in the short-term to ease non-arthritic patellar pain; it is low-cost compared to braces. We want to test the feasibility of a taping intervention as part of a long-term treatment package for PFJOA. Our PPIE group in WP1 of the grant have tried the tape in 2 workshops and been involved in the design of the intervention. They have described the taping as easy to apply at home, comfortable and easy to wear. All these observations may help taping treatment adherence but there are still uncertainties we need to address before progressing to a full clinical trial.

Our aim is for this feasibility trial to answer these uncertainties. This will determine whether patellar taping is a feasible and acceptable part of a treatment package for painful PFJOA.

3. Research Question/Aim(s)

To determine whether patellar taping is feasible and acceptable as part of a best practice care treatment package for painful patellofemoral joint osteoarthritis (PFJOA).

If feasible and acceptable, to plan a full, definitive randomised controlled trial (RCT) to determine long-term clinical effectiveness.

3.1 Objectives

Primary Objective:

i) To assess recruitment (uptake) to the study and retention.

Secondary Objectives:

- ii) To determine whether the tape can be applied by participants correctly at home.
- iii) To assess adherence to the taping intervention.
- iv) To assess how to optimise adherence to taping over an extended period.
- v) To determine participants views about the acceptability of taping.
- vi) To determine whether participants experience a reduction in pain in response to tape.
- vii) To determine a primary outcome for a large scale RCT and to inform the sample size calculation.

3.2 Outcome Measures

Primary outcome

 WP2: To assess recruitment to the study and retention: Participant uptake – number of participants recruited and number of participants who complete the study.

WP3: Report on participant experiences of taping and the trial process. Explore facilitators and barriers to adherence. Evaluate the performance of the participant treatment package.

Secondary outcomes (ii - vii)

- ii) To determine whether the tape can be applied by participants correctly at home: Clinical checks at 2 weeks recorded on the Clinical Report Form.
- iii) Adherence:
 - a. Number of returned or counted unused tapes
 - b. Number of days since the previous timepoint that participants report wearing the tape collected at weeks 2, 6 and 12.
 - c. Average number of hours the participants report wearing the tape daily since the previous timepoint at weeks 2, 6 and 12.
- (iv & v) To assess how to optimise adherence of taping over an extended period and to determine participants views about the acceptability of prolonged taping: Participants interviews in WP3.
- (vi) Effect of intervention: Reduction in pain

- (a) Knee pain measured by VAS_{NA} at baseline, 2, 6 & 12 weeks.
- (b) Knee pain and function measured by KOOS-PF at baseline, 2, 6 & 12 weeks.
- (vii) To determine a primary outcome for a large scale RCT and to inform sample size calculation: Analysis of quantitative data in vi a & b

4. Study Design and Methods of Data Collection

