Participants will be assessed face-to-face at baseline and again face-to-face after 2 weeks and then by telephone or online (e.g. Zoom, Teams) at 6 and 12 weeks. At baseline and weeks 2, 6 and 12 subjects will complete the following assessments: Knee pain during a nominated aggravating activity (VAS_{NA} 0-10), the Knee Osteoarthritis & Injury Outcome Score for the patellofemoral joint (KOOS-PF) (20). Subjects will have a face-to-face assessment 2 weeks after treatment commences to check for correct application of the tape. At this 2 week visit a further 10 weeks of tape will be supplied. At each contact, participants will be asked about treatment adherence. They will be asked since the last timepoint (Baseline, or weeks 2, 6 or 12) approximately how many days per week and how many hours per day on average the tape was worn.

As there is no gold standard for measuring adherence to taping, we will estimate adherence by counting the number of unused strips of tape at the end of the trial and by asking how many days per week and how many hours per day on average the tape was worn. We will collect this information at the 2 weeks tape check and at the two telephone or online consultations at 6 and 12 weeks. Participants will be encouraged to adhere to the tape during the 6-week telephone call. Information on any adverse events will also be collected at each contact.

Work Package 3 (WP3):

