Interviews will explore what went well and any barriers to adherence. This will help evaluate the performance of the participant treatment package. Currently, it is unclear how long taping can be used for effective treatment, so we will explore whether the number of hours of use is associated with a perceived reduction in knee pain and if there is a minimum threshold whereby a how long the tape must be used before any long-term pain reduction. Additionally, as there is no currently available evidence that tape is effective in the long-term specifically for PFJOA, we will explore participant views and willingness to be randomised in a future RCT.

Feasibility and adherence outcomes					
Measure	Stop	Edit	Go		
Number recruited	1 per month	2-3 per month	4 per month		
Percentage recruited (uptake)	< 25%	≥25% and < 75%	≥ 75%		
% of recruited participants with complete data	< 20%	≥20% and < 70%	≥ 70%		
% of recruited participants lost to follow-up at 12 weeks	> 20%	≤20% and ≥10%	< 10%		
% of recruited participants whose pain had clinically improved at 12 weeks	<20%	≥20 and <65%	≥65%		
% of recruited participants who would use the tape again	<20%	≤20 and ≥65%	≥65%		

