4.6 Device in Use

The sports medical tape for this trial is widely used in UK clinical practice and is FDA approved and CE-marked. The tape is approved for use for the treatment of knee pain. It is budgeted for purchase within the study funding stream. Purchase orders will be raised by MFT, product will be shipped, once invoices are paid, to the Stopford Building/or Manchester CRF building and received by the Goods-In Department and delivered to the study team. Sufficient tape will be cut and distributed to the participants at the baseline and 2 weeks visits by the CI along with in person training plus the training materials submitted alongside this protocol. Any excess tape will be disposed of in general waste by the participants at home, information is in the PIS. The advice given will be that participants

should try and wear the tape for as long as is comfortable and taken off at night to be applied fresh the following day. There are no known complications with other treatments being used at the same time.

Manufacturer: We Tape

Brand: Rocktape UK: https://www.rocktape.co.uk

Distributer: c/o Fit Brands Ltd, [name]

This product is a class I medical device and is CE Marked. The CE mark is clearly visible on the outside of the packaging.

The product is made from 97% cotton and 3% nylon, it is hypoallergenic and it does not contain latex.

5. Study Sample and Recruitment

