6.1 Data Analysis

Intervention arm WP2:

All variables will be examined using appropriate descriptive statistics (mean [standard deviation], median [interquartile range], n [%]) and graphics for completeness and form. No imputation will be made for missing data, however quantities and location will be used to inform the design of a future RCT.

The primary outcome, recruitment rate, will be presented as a proportion with 95% binomial confidence intervals. This will also be presented on a monthly basis. Other feasibility parameters, dropout rates and those with complete data, will be presented similarly.

Adherence, i.e. number of returned tapes and the number of days and average hours of daily usage, will be reported for each timepoint as continuous measures with mean/median and SD/IQR as appropriate. Overall measures of usage will be presented and comparative statistics or line graphs will illustrate any changes in usage over the study duration. It is possible there may be reasons other than non-adherence which result in unused tapes (e.g. major increases or decreases in symptoms). We will collect this information at the 2 weeks clinical check, at the two telephone consultations at 6 and 12 weeks, and during the qualitative study WP3. Further prompts to encourage tape adherence will be done during the telephone consultations using the questionnaires at 6 and 12 weeks.

Adverse events (such as skin irritation, the development of new pain in other body regions thought to be related to the interventions) will be presented as the total number and proportion.

The measures of treatment efficacy, pain scale (VAS_{NA} 0-10) and the Knee Osteoarthritis & Injury Outcome Score for the patellofemoral joint (KOOS-PF) (20) will be reported with descriptive statistics and graphics at baseline, 2, 6 and 12 weeks. Preliminary analysis of all timepoints alongside the change from baseline to 12 weeks will be presented to inform the design of the future full RCT. The KOOS-PF will be scored as per validated instructions (20). This includes a "rule" that a subscale score can be calculated if 50% or more of the items in specific subscale have been completed by the participant.

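### Days worn is defined both as a count over unequal intervals and as a weekly rate, unused strips have no denominator, and the progression table has no row for wear or correct application

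*Protocol*

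**What the plan says.** **Days worn.** Section 3.2, item iii(b), defines the outcome as "Number of days since the previous timepoint that participants report wearing the tape collected at weeks 2, 6 and 12". The endpoint column of the Study Summary also gives a number of days. The outcome column of the same summary gives "number of days per week worn and the average hourly use", and section 4.2 says twice that participants will be asked for days per week.

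**Hours worn.** Section 3.2, item iii(c), uses "Average number of hours the participants report wearing the tape daily since the previous timepoint at weeks 2, 6 and 12", which is already a rate.

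**Tape count.** The Study Summary and section 3.2 allow unused tapes to be either returned or counted; the Study Summary places this at weeks 2, 6 and 12. Section 4.2 mentions a count at the end of the trial, then says the information is collected at weeks 2, 6 and 12. Supply is two weeks of tape at baseline, then: "At this 2 week visit a further 10 weeks of tape will be supplied". Weeks 6 and 12 are telephone or online contacts. Section 4.6 says "Any excess tape will be disposed of in general waste by the participants at home".

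**Analysis.** Under section 6.1, "number of returned tapes and the number of days and average hours of daily usage, will be reported for each timepoint as continuous measures". Comparative statistics or line graphs then show how usage changes over the study.

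**Progression.** The Stop/Edit/Go table in section 4.2 is headed "Feasibility and adherence outcomes". Its six rows are number recruited, uptake, complete data, loss to follow-up, pain improvement and willingness to use the tape again. The Background says a definitive trial must be informed by "evidence that patients with PFJOA can apply the tape, and that they will wear it over an extended period".

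**The concern.** Adherence is secondary objective iii, and poor adherence to a knee brace is the protocol's own reason for trying tape. The question for the future trial is whether wear holds up or fades over 12 weeks. A count taken over intervals that lengthen from 2 to 4 to 6 weeks rises when behaviour is constant and can rise when wear is falling. A count of strips left from a 10-week issue is high at week 6 simply because most of that tape is not yet due. An analyst following sections 3.2 and 6.1 to the letter would plot those quantities; one following section 4.2 would plot a different variable under the same outcome name.

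The progression table raises a separate problem. Its heading promises adherence, but no row measures wear or correct application, so the formal decision does not use the evidence the Background asks for.

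**Working it through.** The protocol gives no numerical figure for adherence, so there is none to reproduce. The check is arithmetic on its schedule.

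**Inputs from the protocol.** Contacts at weeks 2, 6 and 12, each ±5 days (section 4.4). Tape used daily for 12 weeks, two strips applied, two weeks of tape at baseline and ten weeks at week 2 (section 4.2). Sample of 30 (section 5.3.1).

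**Assumptions.** One application a day and no spare strips, which gives 2 × 14 = 28 strips at baseline and 2 × 70 = 140 at week 2. The protocol states neither total. Leftovers from the first supply are set aside.

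**1. Interval lengths.** Nominally 14, 28 and 42 days, a ratio of 1:2:3. With the windows, the first can be 9 to 19 days. The second can be 28 ± 10 = 18 to 38 and the third 42 ± 10 = 32 to 52, because both ends can move.

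**2. Day count = days per week × weeks in the interval.**

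| True wear (days/week) | Week 2 | Week 6 | Week 12 |
|---|---|---|---|
| Constant 7 | 14 | 28 | 42 |
| Constant 5 | 10 | 20 | 30 |
| Constant 3 | 6 | 12 | 18 |
| Falling 7, 5, 4 | 14 | 20 | 24 |

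Constant wear looks like a threefold rise, and the real fall also looks like a rise. Conversely, a flat count of 14 would mean 14/2 = 7, 14/4 = 3.5 and 14/6 = 2.3 days a week. Within one timepoint, two people who both wear tape every day could report 18 and 38 days at week 6 because of the windows alone.

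**3. Unused strips = strips issued − 2 × days worn from that supply.**

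- Perfect wear: 28 − 28 = 0 at week 2; 140 − 56 = 84 at week 6; 140 − 140 = 0 at week 12.
- Constant 5 days a week: 28 − 20 = 8; 140 − 40 = 100; 140 − 100 = 40.

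In both cases the count jumps at week 6 and falls again while behaviour does not change.

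**4. The same data as rates.** For constant 5 days a week, days worn over days elapsed is 10/14, 20/28 and 30/42. Strips used over strips due is 20/28, 40/56 and 60/84. Every one of these equals 5/7, or 71%, so the series is flat, as it should be.

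**5. The Go column with 30 recruited.** Complete data: 0.70 × 30 = 21 or more. Lost to follow-up: fewer than 3, so at most 2. Pain improved and would use again: 0.65 × 30 = 19.5, so 20 or more each. Add four recruited per month and at least 75% uptake. None of these conditions contains days, hours, strips or the week 2 application check.

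**The case against.** The strongest reply is that much of the protocol already uses a rate. Hours are a daily average. The Study Summary's outcome column and section 4.2 use days per week, so the question described as put to participants does not depend on interval length. Interval dates and tape issued will be known, so counts can be rescaled, and an analysis plan not shown here might say so. That stands against one tempting inference, that all the adherence trends will be artefacts: the documents support this only for the day count if left unscaled and for raw unused strips. It does not remove the contradiction, because section 3.2 defines a count and section 6.1 carries a number of days into the comparison over time.

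Two further readings should be resisted. A reader might take section 4.2 to place the tape count only at the end of the trial, but the text goes on to collect the information at weeks 2, 6 and 12. A reader might also infer that tape will be thrown away before it is counted. Section 4.6 gives no timing for disposal and points to the information sheet, which is not at hand. What remains is that disposal and counting are not tied together.

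On the table, it can fairly be said that the Background asks for a trial informed by this evidence, not gated on it. There is no gold standard for adherence to taping, section 4.6 advises wear for as long as is comfortable, and the pain and use-again rows give some indirect restraint. That restraint is weak. Everyone also receives exercise instruction and best-practice advice, there is no control group, and entry requires a pain score of at least 4, so pain scores may fall with little tape worn. The protocol does not say how the rows combine, so it would be too strong to say the plan prescribes a Go despite poor wear. It only fails to prevent one.

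**Conclusion.** The point holds as an inconsistency in the adherence definition together with an omission from the progression table.

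- Days worn has two incompatible definitions. Under the count version, constant wear shows a threefold rise across the three contacts, and a fall from 7 to 4 days a week can appear as an increase. This rests only on the nominal schedule.
- Raw unused-strip counts are not comparable across contacts. The 0, 84 and 0 pattern assumes two strips a day, one application and no spares; spare strips would change the figures but not the fault.
- Average hours per day is sound.
- Every Go row can be met whatever the wear, and none covers correct application.

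These are secondary, descriptive outcomes, and the primary outcome of recruitment and retention is untouched. They nevertheless bear on what the protocol says the future trial needs to know, so they should be corrected.

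**What to change.** 1. Put one rate-based definition in section 3.2, both columns of the Study Summary and section 6.1: days worn divided by days since the last contact (or days per week), and strips used divided by strips due since the last contact. Record the actual contact dates and the number of strips issued so that both denominators are known.
2. In section 6.1, say returned or counted, as the Study Summary and section 3.2 do.
3. Reconcile home disposal in section 4.6 with the planned counts at weeks 6 and 12 by stating, there and in the information sheet, that excess tape is kept until the final count.
4. Add two rows to the progression table: adherence, expressed as the rate above, and the percentage applying the tape correctly at the week 2 check before any correction. The sponsor should set the cut-offs in advance and give its reasons; the bands for the existing rows were set for other quantities and should not simply be borrowed.

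The cost is wording in the protocol, information sheet and case report form. Wear, tape counts and the application check are already planned at existing contacts, so no visit or call is added.
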